10.3.2.2 Sensitivity Analyses for Missing Data

Subjects with missed visit, lost to follow-up or patency grade ‘unable to view’ by the independent reviewer will be considered as missing data. If more than 10% of the primary efficacy data are missing, the following imputation analyses will be performed to assess the sensitivity of conclusions to missing data from the independent reviewer:

- Impute ‘4’, for all missing values on the control sides and ‘0’ on the treatment sides; this is a worst-case imputation.
- Impute ‘0’, for all missing values on the control sides and ‘4’ on the treatment sides; this is a best-case imputation.
- A “tipping point” analysis in which all missing observations on the control side will systematically be assigned a 0, 1, 2, 3 or 4, and all missing observations on the treatment side will separately be assigned a 0, 1, 2, 3, or 4, for a total of $5 \times 5 = 25$ analyses.
- Impute patency grades at Day 30 by clinical investigators in subjects missing values on the control or treatment sides.

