9.4.2 Randomized Cohort

The sample size was calculated based on the difference in the patency grade at Day 30 between the treatment and control sides with the following assumptions:

- Expected mean difference of 0.5 between the treatment and control sides in patency grade
- A SD of 1.1 for side-to-side difference in the patency grade of the FSO
- Target power of $\geq 90\%$
- Type I error rate of $\alpha = 0.05$, 2-sided

A mean difference in patency grade of 0.5 between the treatment and control sides favoring treatment sides was considered clinically meaningful. Based on standard formulas for a paired t-test, a sample size of 53 subjects provides at least 90% power to detect a difference of 0.5 in mean patency grade between treatment sides. Assuming up to 25% of subjects with non-evaluable data on one or both sides, additional 17 subjects will be enrolled for a total of 70 subjects in the randomized cohort.

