10.3.2 Randomized Cohort – Primary Efficacy Endpoint

The primary efficacy endpoint is the difference in patency grade of the FSO between the treatment and control sides at Day 30 as determined by an independent, blinded sinus surgeon based on the centralized video-endoscopy review. Patency of the FSO will be assessed endoscopically by probing with a 3-mm olive-shaped frontal sinus suction tip (“suction tip”) and will be analyzed using the paired t-test.

For each subject, the difference in patency grade of the FSO between the treatment and control sides will be calculated and then averaged across all subjects. The difference in patency grade for a given subject will be set as missing if one of the FSO is unable to be viewed or graded.

The primary efficacy hypothesis is that mometasone furoate (MF) from the UP Drug-Coated Device will significantly increase the patency grade on the treatment side compared to control. The statistical test will be paired t-test where the difference in patency grade between treatment and control sides is determined.

The relevant null and alternative hypotheses for this primary efficacy endpoint are:

- $H_0: \mu = 0$
- $H_1: \mu \neq 0$

where μ is the mean difference in the FSO patency grade between the treatment and control sides at Day 30. The study will be considered successful if there is a statistically significant difference in the mean patency grade in favor of the UP Drug-Coated Device.

Although the alternative hypothesis is specified as two-sided, only a statistically significant difference in patency grade favoring treatment sides will constitute evidence of effectiveness. The two-sided α for this test is 0.05 (or one-sided α of 0.025).

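### The SAP's tipping-point grid fills missing grades with whole-grade constants counted as observed data, so it brackets the tipping point only to within a grade and gives p-values near no effect that are too small

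*SAP*

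**What the plan says.** The primary comparison is specified in SAP 10.3.2: "The statistical test will be paired t-test where the difference in patency grade between treatment and control sides is determined". The level is 0.05 two-sided, and a subject's difference is missing if either side cannot be viewed or graded.

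SAP 9.4.2 gives the design values: "Expected mean difference of 0.5 between the treatment and control sides in patency grade" and "A SD of 1.1 for side-to-side difference in the patency grade of the FSO". It allows for substantial missing data, "Assuming up to 25% of subjects with non-evaluable data on one or both sides", and raises the target from 53 to 70 to cover this.

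SAP 10.3.2.2 counts missed visits, loss to follow-up and ungradable videos as missing. Above 10% missing it plans four analyses: a worst-case fill, a best-case fill, a tipping-point grid, and substitution of the investigator's Day 30 grades. In the grid, "all missing observations on the control side will systematically be assigned a 0, 1, 2, 3 or 4", and missing treatment sides are likewise given one whole grade, for 25 analyses. The section specifies no residual variation, no multiple imputation, and no rule for reading the 25 results.

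**The concern.** A tipping-point analysis should show how unfavourable the unseen outcomes must be before the conclusion changes, with uncertainty that reflects their being unseen. This grid falls short in two ways.

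- **Precision.** Identical filled values enter the t-test as observed pairs. Filling with no difference pulls the mean towards zero, but it also shrinks the SD and restores the full sample size, so t hardly moves.
- **Resolution.** When a subject lacks both sides, only the treatment fill minus the control fill matters. That takes 9 values, from -4 to +4, one grade apart, while the trial is designed around half a grade.

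The grid is the only graded stress test of the primary result against missing data. The planned allowance, 17 of 70 (24.3%), is well above the 10% trigger, so at the planned rate it would be run and cited. A borderline result could be reported as robust to a no-effect assumption when a proper analysis would say otherwise.

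**Working it through.** **Plan's own figure.** Exact noncentral-t power for a paired t-test with mean 0.5, SD 1.1 and two-sided 0.05 is 0.895 at n = 52 and 0.901 at n = 53. This reproduces the statement that "a sample size of 53 subjects provides at least 90% power to detect a difference of 0.5 in mean patency grade between treatment sides".

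**Inputs.** From SAP 9.4.2: SD s = 1.1, design mean 0.5, N = 70, m = 17 missing at the planned allowance. From SAP 10.3.2.2: the trigger of more than 10%, so m = 8 (11.4%) is the first count above it, counting subjects. Assumed: an observed mean d of 0.5 (design) or 0.31 (borderline), and both sides missing. Let n = N - m and let k be the filled treatment-minus-control difference.

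**Constant fill.**
- Mean = (n·d + m·k)/N
- SS = (n - 1)s² + (nm/N)(d - k)²
- SE = √[SS/(N - 1)]/√N

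For m = 17, d = 0.31, k = 0:
- Mean = 16.43/70 = 0.235
- SS = 52 × 1.21 + 12.871 × 0.0961 = 64.16
- SE = √(64.16/69)/√70 = 0.115
- t = 2.04, p = 0.0455

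The complete-case result is 0.31/(1.1/√53) = 2.05, p = 0.0453.

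For d = 0.5, k = 0: mean 0.379, SS = 62.92 + 3.22 = 66.14, SE 0.117, p = 0.0019 (complete-case 0.0017). With all 70 pairs observed the SE would be 1.1/√70 = 0.131, so this fill makes the trial look more precise than if nothing were missing.

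**Multiple imputation centred on the same k.** This uses normal imputation with residual variance, no predictors, Rubin's rules and a large-sample reference:
- s₂ = s²(n - 1)/(n - 3)
- U = [(n - 1)s² + m·s₂ + (nm/N)(d - k)²]/[N(N - 1)]
- B = (m/N)²(s₂/m + s₂/n)
- SE = √(U + B)

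For m = 17, d = 0.31, k = 0:
- s₂ = 1.258
- U = (62.92 + 21.39 + 1.24)/4830 = 0.01771
- B = 0.00577
- SE = 0.153, z = 0.235/0.153 = 1.53, p about 0.13

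For d = 0.5: SE about 0.155, p about 0.014 by formula and 0.015 by simulated imputation.

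| Missing pairs | Observed mean | Complete-case p | No-effect constant fill p | No-effect imputation p |
|---|---|---|---|---|
| 17 | 0.50 | 0.0017 | 0.0019 | about 0.015 |
| 17 | 0.31 | 0.0453 | 0.0455 | about 0.13 |
| 8 | 0.50 | 0.0007 | 0.0007 | about 0.0018 |
| 8 | 0.31 | 0.0302 | 0.0304 | about 0.05 |

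**Resolution, constant fill at the design values.**

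| Missing pairs | p at k = 0 | p at k = -1 | p at k = -2 | Constant-fill tip, solved continuously |
|---|---|---|---|---|
| 8 | 0.0007 | 0.019 | 0.175 | -1.38 |
| 10 | 0.0009 | 0.041 | 0.38 | -1.07 |
| 11 | 0.0010 | 0.058 | 0.51 | -0.95 |
| 17 | 0.0019 | 0.33 | 0.54 | -0.53 |

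The corresponding multiple-imputation tips are about -1.22 with 8 missing and -0.29 with 17 missing. Constant filling therefore also places the tip further from zero than it should be.

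**One side missing.** The observed side keeps its own grade, so the filled differences vary. Grades of 0 to 4 were simulated (mean difference 0.52, SD 1.21, 600 trials per pattern, 17 missing). Among trials significant on complete cases, the -1 cells stayed significant in about 12% when both sides were missing, 30-40% when half the missing subjects lacked one side only, and 45-75% when all did.

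**The case against.** A reader might infer that the grid cannot locate a tipping point, or that the first step below zero always destroys a positive result. The documents support neither.

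- The grid brackets the tip to within one grade: between 0 and -1 with 17 missing, between -1 and -2 with 8.
- At the design values the -1 cell survives with 8 to 10 missing pairs and fails only from 11. This depends on the observed mean: at 0.4 with 8 missing, -1 already gives p = 0.079, while at 0.6 with 10 missing it gives 0.009. The grid does separate fragile from robust results.
- The SE is not too small against the full-data 0.131 everywhere. With 17 missing and mean 0.5 it is 0.138 at -1 and 0.172 at -2. These remain below the imputation values of 0.171 and 0.200.
- The SAP expressly anticipates subjects missing one side only, where the fills are not constant differences.
- Patency is graded in whole numbers, so each fill is a grade that could be assigned.
- The success criterion is the primary t-test; nothing in the SAP makes success depend on the grid.

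All of this stands and limits the point. It does not answer the precision problem at and near no effect for missed visits and losses to follow-up. The other planned analyses do not fill the gap. The best- and worst-case fills are extreme bounds. Investigator-grade substitution preserves natural variability, but it needs a Day 30 visit and applies no shift.

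**Conclusion.** The point holds in a limited form. The grid is coarse, bracketing the tip only to within a grade, and its p-values at and near no effect are too small. The size depends on the amount missing. At the planned allowance of 17 pairs, a borderline result (mean 0.31) reads as p = 0.0455 under no effect when about 0.13 is appropriate, which reverses the robustness reading. At the design mean, p is understated (0.0019 against about 0.015) but the conclusion stays. With 8 missing the borderline comparison is 0.030 against about 0.05.

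These figures assume SD 1.1, both sides missing, and imputation without predictors; informative Day 14 grades would narrow the gap. The primary test and its type I error are unaffected. This is a worthwhile, inexpensive improvement to a supporting analysis.

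**What to change.** In SAP 10.3.2.2, make the tipping-point analysis a delta-adjusted multiple imputation of the reviewer's Day 30 grades:

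- Use as predictors the reviewer's Day 14 grades and, where one side was graded at Day 30, that observed grade.
- Impute with residual variance and combine by Rubin's rules.
- Shift the imputed treatment-minus-control difference in steps of 0.25 grade or finer, from the missing-at-random estimate through no effect to -2. The range must start above zero because a borderline result can tip before no effect is reached.
- Report the mean imputed difference at which two-sided p crosses 0.05.

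Keep the best-case, worst-case and investigator-grade analyses. Keep the 5 x 5 grid only as a descriptive supplement.

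The cost is SAP wording and some extra programming. The Day 14 reviewer grades are already planned, so no new data are needed. The change should precede database lock so that it counts as a priori under SAP 9.2. The sponsor should expect sensitivity p-values near no effect to be less favourable.

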10.4 Secondary Endpoints

10.4.1 PK Cohort

10.4.1.1 Endoscopic Outcomes Assessed by Clinical Investigators

Categorical measures will be analyzed as counts, proportions and frequencies and, where appropriate, 95% CI will be computed using exact methods.

The counts, proportion and frequency of the following outcomes will be presented per sinus side:

- Patency grade: sinuses with clinically significant stenosis/occlusion in the FSO (patency grade 0 or 1).

- Adhesion/scarring grade: sinuses with clinically significant amount of adhesion/scarring in the frontal recess/FSO (adhesion/scarring grade 2 or 3)
- Polypoid edema grade: sinuses with clinically significant amount of polypoid edema in the frontal recess/FSO (polypoid edema grade 2 or 3)
- Need for post-dilation intervention: proportion of sinuses that need post-dilation interventions in the frontal recess/FSO (e.g., steroid, surgical, repeat balloon dilation).

Post-dilation intervention is a composite endpoint that includes:

- Surgical interventions required to debride obstructive adhesions or scar tissue formation in the FSO (adhesion/scarring grade 2 or 3), and/or
- Oral steroid interventions warranted to resolve recurrent inflammation or polypoid edema in the frontal recess/FSO, and/or
- Repeat balloon dilation warranted to resolve clinically significant stenosis/occlusion of the FSO (patency grade 0 or 1)

Additional grouping for the above variables will also be analyzed.

Continuous measures will be analyzed using descriptive statistics such as means, SD, and, where appropriate, 95% CI, assuming a normal distribution for each timepoint. A change from baseline in patency, estimated FSO diameter, polypoid edema and inflammation score will be computed for each treated sinus.

10.4.1.2 Patient Reported Outcomes

The total SNOT-22 scores and individual domain scores will be computed. The total score is calculated as the sum of all 22 items, and ranges from 0 to 110, with the higher scores being worse outcome. The following table lists items and ranges for each symptom domain score.

SNOT-22 Domains	Survey Items	Score Range
Rhinologic Symptoms	#1, #2, #3, #6, #21, #22	0–30
Extra-Nasal Rhinologic Symptoms	#4, #5, #6	0–15
Ear/Facial Symptoms	#2, #7, #8, #9, #10	0–25

SNOT-22 Domains	Survey Items	Score Range
Psychological Dysfunction	#14, #15, #16, #17, #18, #19, #20	0–35
Sleep Dysfunction	#11, #12, #13, #14, #15	0–25

10.4.2 Randomized Cohort

10.4.2.1 Endoscopic Outcomes Assessed by Independent Reviewer

Descriptive statistics such as means, SD, median and, where appropriate, 95% CI will be computed for all continuous measures. Paired t-test will be used to assess side-to-side differences between treatment sides.

Descriptive statistics and side-to-side differences between treatment and control sides will be analyzed for the following outcomes:

- Patency grade of the FSO at Day 14
- Polypoid edema grade of the FSO at Day 14 and Day 30
- Estimated largest diameter of the FSO at Day 14 and Day 30
- Inflammation in the frontal recess/FSO at Day 14 and Day 30

Categorical measures will be analyzed as counts, proportions and frequencies and, where appropriate, 95% CI will be computed. Categorical data that can be localized to the treatment or control side will be analyzed using McNemar's test for correlated proportions. An exact version of McNemar's test will be performed for correlated proportions.

Counts, proportions and frequencies and side-to-side differences between treatment sides will be analyzed for the following categorical measures by independent reviewer at Day 14 and Day 30:

- Patency grade: sinuses with clinically significant stenosis/occlusion in the FSO (patency grade 0 or 1).
- Adhesion/scarring grade: sinuses with clinically significant amount of adhesion/scarring in the frontal recess/FSO (adhesion/scarring grade 2 or 3)
- Polypoid edema grade: sinuses with clinically significant amount of polypoid edema in the frontal recess/FSO (polypoid edema grade 2 or 3)

- Need for post-dilation intervention: proportion of sinuses that need post-dilation interventions in the frontal recess/FSO (e.g., steroid, surgical, repeat balloon dilation).

Additional grouping for the above variables will also be analyzed.

10.4.2.2 Endoscopic outcomes assessed by clinical investigators

Descriptive statistics such as means, SD, median and, where appropriate, 95% CI will be computed for all continuous measures. A paired t-test will be used to assess side-to-side differences between treatment and control sides. Descriptive statistics and side-to-side differences between treatment sides through Day 60 will be analyzed for the following:

- Patency grade of the FSO
- Polypoid edema grade of the frontal recess/FSO
- Estimated largest diameter of the FSO
- Inflammation in the frontal recess/FSO

Categorical measures will be analyzed as counts, proportions and frequencies and, where appropriate, 95% CI will be computed. Categorical data that can be localized to the treatment or control side will be analyzed using McNemar's test for correlated proportions. An exact version of McNemar's test will be performed for correlated proportions.

Counts, proportions and frequencies and side-to-side differences between treatment sides will be analyzed for the following categorical measures by clinical investigators through Day 60:

- Patency grade: sinuses with clinically significant stenosis/occlusion in the FSO (patency grade 0 or 1).
- Adhesion/scarring grade: sinuses with clinically significant amount of adhesion/scarring in the frontal recess/FSO (adhesion/scarring grade 2 or 3)
- Polypoid edema grade: sinuses with clinically significant amount of polypoid edema in the frontal recess/FSO (polypoid edema grade 2 or 3)
- Need for post-dilation intervention: proportion of sinuses that need post-dilation interventions in the frontal recess/FSO (e.g., steroid, surgical, repeat balloon dilation).

Additional grouping for the above variables will also be analyzed.

10.5 Consistency Across Study Centers

The consistency of device performance across the study centers will be investigated. A one-way analysis of variance (ANOVA) will be used to test whether the mean difference in patency grade between treatment and control sides differs by site. If a statistically significant site effect is not found ($p > 0.05$), results will be considered poolable across sites. If a statistically significant site is found ($p < 0.05$), exploratory analyses will be conducted to investigate the issue. This may include regression adjustment for baseline clinical characteristics; the set of baseline characteristics to be considered include those that significantly differ across sites, or significantly predict the difference in patency grade between the treatment sides. If regression adjustment causes the site term to become non-significant, results will be considered poolable across sites, and covariate-adjusted estimates of the treatment effect will be reported. If regression adjustment does not explain the site heterogeneity, further summaries (separating sites or excluding sites) will be explored.

10.6 Multiplicity Adjustment for Secondary Efficacy Endpoint Analyses

The company intends to present inferential statistical results in the clinical summary section of the instructions for use for 4 secondary endpoints. This section describes the methods that will be used to control the familywise type 1 error rate (FWER) among the tests of these 4 secondary endpoints.

If and only if the primary efficacy objective of the randomized cohort is met, Holm's step-down procedure will be used to control the FWER at a one-sided significance level of 0.025 for the following 4 secondary endpoints:

- Difference in the mean polypoid edema grade of the frontal recess/FSO between the treatment and control sides at Day 14 by independent reviewer
 - Test: $H_0: \mu_t = \mu_c$ vs $H_A: \mu_t < \mu_c$, by paired t-test
- Difference in mean estimated largest diameter of the FSO between the treatment and control sides at Day 30 by independent reviewer
 - Test: $H_0: \mu_t = \mu_c$ vs $H_A: \mu_t > \mu_c$, by paired t-test

- Difference in the proportion of clinically significant amount of stenosis/occlusion in the FSO (grade 0 or 1) between the treatment and control sides at Day 30 by independent reviewer
 - Test: $H_0: P_T = P_c$ vs $H_A: P_T < P_c$, by McNemar's test (exact version)
- Difference in the mean estimated largest diameter of the FSO between the treatment and control sides at Day 60 by clinical investigators
 - Test: $H_0: \mu_T = \mu_c$ vs $H_A: \mu_T > \mu_c$, by paired t-test

Let $p_{(1)} \leq p_{(2)} \leq \dots \leq p_{(m)}$ be the $m=4$ p-values resulting from the above 4 tests, after being placed in ascending order. Adjusted p-values $\tilde{p}_{(1)}, \dots, \tilde{p}_{(m)}$ from Holm's step-down procedure will be calculated as follows:

$$\tilde{p}_{(i)} = \begin{cases} mp_{(1)} & \text{for } i = 1 \\ \max\left(\tilde{p}_{(i-1)}, (m-i+1)p_{(i)}\right) & \text{for } i = 2, \dots, m \end{cases}$$

Source: SAS Institute Inc. 2008. *SAS/STAT® 9.22 User's Guide*. Cary, NC: SAS Institute Inc., p 4839.

If any adjusted p-value exceeds 1, it is set to 1. Using this procedure, any adjusted one-sided p-value that is < 0.025 is statistically significant and supports a claim for the corresponding endpoint, while any adjusted p-value ≥ 0.025 is not statistically significant. Both adjusted and unadjusted p-values will be reported. (Cook 1998)

10.7 Safety Measures

In the PK cohort, continuous data from the plasma MF, plasma cortisol and 24-hour urinary cortisol concentrations will be expressed using descriptive statistics, including but not limited to, mean, SD, medians, ranges and, where appropriate, coefficient of variation as described in [Section 9.3.1](#).

Adverse events will be coded using the Medical Dictionary for Regulatory Activities (MedDRA). Where possible, and if applicable, AE will be localized to a sinus type and side. If a subject reports the same AE more than once or experiences the same AE on multiple occasions, the maximum severity grade and relationship to the study drug, study device, accessory devices, and/or dilation procedure will be presented.

The incidence and percentages of AE and serious adverse events (SAE) through Day 30 in the PK cohort and through Day 60 in the randomized cohort, including adverse device effects and USADE, will be presented by MedDRA system organ class (SOC) and preferred term (PT). Complete subject listings of all AE will be provided. For each AE, the following will be specified:

- Start and stop dates, and event onset (study day)
- The affected side (right or left) if available
- Seriousness
- Severity
- Strength of relationship
- Action taken
- Outcome

10.8 Concomitant Medications

Prior and concomitant medications will be coded to therapeutic class and PT using the WHO Drug Global dictionary. All concomitant medications will be listed and summarized in a table.

12 APPENDICES

Appendix A: Schedule of Assessments

PK Cohort

Assessment	Screening	Baseline/ Procedure	Day 1	Day 3	Day 7 (±2 d)	Day 14 (±2 d)	Day 21 (±2 d)	Day 30 (±3 d)
Informed consent	X							
Medical/surgical history	X							
CT scan (≤ 30 days prior to enrollment)	X							
Blood sample collection (~11 ml)		X ^a	X ^b	X ^b	X ^b	X ^b		X ^b
24-hour urine collection		X ^c	X ^c					
In-office bilateral FSO dilation		X						
Endoscopic grading and recording	X	X ^d			X	X	X	X
Sino-Nasal Outcome Test (SNOT-22)		X ^d				X		X
Concomitant medications	X	X	X	X	X	X	X	X
Adverse event reporting	X	X	X	X	X	X	X	X
Urine pregnancy test (female subjects of childbearing potential)	X ^{e,f}	X ^{e,f}						
Documented birth control (female subjects)			X	X	X	X	X	X

Abbreviations: CT, computed tomography; d, days; FSO, frontal sinus ostium/ostia; min, minutes; ml, milliliter.

- ^a Blood draws to occur at baseline, before balloon dilation procedure and again at Hour 0.5 (±5 min), 1 (±5 min), 2 (±10 min), and 4 (±15 min) after the end of baseline procedure
- ^b All blood draws should occur in the morning and at approximately the same time of the day during the follow-up visits. Day 1 blood draw to occur 24 hours (±3 hours) after the baseline procedure. Day 3 blood draw to occur 72 hours (±3 hours) after the baseline procedure
- ^c Urine samples will be collected for a 24-hour duration prior to the baseline visit (pre-procedure) and for a 24-hour duration following the baseline procedure (post-procedure)
- ^d All endoscopic assessments and SNOT-22 performed prior to the baseline procedure, except for the FSO diameter, which must be performed before and after the balloon dilation procedure.
- ^e Female subjects with reproductive potential are required to undergo a urine pregnancy test at screening and prior to the baseline procedure.
- ^f Female subjects are required to confirm their nursing status at screening and baseline

Randomized Cohort

Assessment	Screening	Baseline/ Procedure	Day 7 (±2 d)	Day 14 (±2 d)	Day 21 (±2 d)	Day 30 (±2 d)	Day 60 (±3 d)
Informed consent	X						
Medical/surgical history	X						
CT scan (≤ 30 days prior to randomization)		X					
In-office bilateral FSO dilation		X					
Endoscopic grading and recording	X	X ^a	X	X	X	X	X
Video-endoscopy grading (independent reviewer)				X		X	
Concomitant medications	X	X	X	X	X	X	X
Adverse events reporting	X	X	X	X	X	X	X
Urine pregnancy test (female subjects of childbearing potential)	X ^{b,c}	X ^{b,c}					
Documented birth control (female subjects)			X	X	X	X	X

Abbreviations: CT, computed tomography; d, day; FSO, frontal sinus ostium/ostia.

^a All endoscopic assessments performed prior to baseline procedure

^b Female subjects with reproductive potential are required to undergo a urine pregnancy test at screening and prior to the baseline procedure.

^c Female subjects are required to confirm their nursing status at screening and baseline

